9.3 Data Collection

FEV1, FVC, and pulse oximetry will be obtained for all patients at 4 different time points: (1) baseline measurement at the time of enrollment; (2) preoperatively on the day of surgery; (3) immediate postoperative period 24 hrs after surgery; and (4) delayed postoperative period on postoperative day 3. The digital spirometer couples with a HIPAA-compliant mobile app which stores data and shares it with the research team via a HIPAA-compliant dashboard. These data will be used to assess compliance with the intervention for the digital group both in the preoperative and postoperative period. Sustained accelerometer movement data will be used as a surrogate for frequency of use and will be

used to assess compliance with the intervention for the standard group in the postoperative period.

9.4 Endpoints

The primary endpoint is FEV1 change at day-of-surgery preoperative from baseline. The secondary endpoints include FVC and pulse oximetry change at day-of-surgery preoperative from baseline, change in FEV1, FVC and pulse oximetry at preoperative day 3 from day 1. Exploratory Endpoints are daily frequency of IS use and postoperative complications defined my Modified Accordion Grading System (MAGS).³⁹

9.5 Sample Size/Power Analysis

The sample size calculation is based on the primary outcome only. Previous research has shown that the mean difference in FEV1 between control and preoperative incentive spirometry intervention groups is 0.4 L with a standard deviation of 0.6.²⁸ Bonferroni correction will be used for three-group comparisons. Sample sizes of 49 per group achieve 80.6% power to detect the difference in FEV1 assuming a mean difference of 0.4 L and a standard deviation of 0.6 at a significance level of 0.017 using a two-sided, two-sample, equal-variance t-test. To account for a 5% dropout rate, we will enroll 52 patients per group for a total of 156 patients enrolled in the study.

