Objectives:	
Primary Objective: To determine the efficacy of incentive spirometry to improve FEV1 in the preoperative surgical setting.
 
Secondary Objectives:
 
 1. To determine the efficacy of incentive spirometry to improve FVC and pulse oximetry in the preoperative surgical setting. 2. To determine the change in FEV1, FVC and pulse oximetry after surgery. 
Exploratory Objectives:
 
 1. To determine the daily number of times patients perform incentive spirometry in the preoperative and postoperative setting. 2. To determine whether standard incentive spirometers move throughout a patients' postoperative stay using accelerometers, as a proxy for how often patient uses the device. 3. To evaluate whether a digital IS device + text message based mobile health intervention will improve FEV1, FVC, and pulse oximetry compared to standard IS. 4. To evaluate the rate of pulmonary complications across the 3 preoperative groups.
Endpoints:	
Primary Endpoint: Change in FEV1 at day-of-surgery preoperative from baseline
 
Secondary Endpoints:
 
 1. Change in FVC and pulse oximetry at day-of-surgery preoperative from baseline 2. Change in FEV1, FVC and pulse oximetry at postoperative day 3 from day 1

	
Exploratory Endpoints:
 
 1. Daily frequency of digital IS use. 2. Movement data of standard IS with accelerometers (this is a proxy endpoint for IS use). 3. Difference in changes in FEV1, FVC, and pulse oximetry between randomized groups. 4. Postoperative complications defined by Modified Accordion Grading System (MAGS)
Study Population:	We plan to enroll 156 adult patients who are scheduled to undergo major abdominal surgery with an expected postoperative hospital stay of \geq 48 hours.
Phase:	N/A
Description of Sites / Facilities Enrolling:	The study will take place at Barnes Jewish Hospital system/Washington University School of Medicine.

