9.0 STATISTICAL CONSIDERATIONS

9.1 Study Design

This is a prospective, single-center, randomized trial. The enrolled patients will be randomized 1:1:1 to one of three groups: control, standard IS, and digital IS + text message. They will have baseline measurement at the time of randomization, and pre-operative measurement after randomization and before the surgery. After surgery, patients will be re-randomized to either standard IS or digital IS + text message. Measurements at post-op days 1 and 3 will be taken. The primary objective of this study is to determine the efficacy of incentive spirometry to improve FEV1 in the preoperative setting. The secondary objectives are to determine the efficacy of incentive spirometry to improve FVC and pulse oximetry in the preoperative setting, and FEV1, FVC, and pulse oximetry in the postoperative setting. The exploratory objectives are to determine the daily number of times patients perform incentive spirometry in the postoperative setting and evaluate the rate of pulmonary complications across the 3 preoperative groups.

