9.6 Data Analysis

The analysis will be intent-to-treat approach. The FEV1, FVC and pulse oximetry changes at day-of-surgery preoperative from baseline will be compared across three groups using ANOVA or Kruskal-Wallis test, as appropriate. The linear regression model will be considered to adjust for the other interested variables including age, sex, smoking status, BMI, ASA, and malignancy. The same analysis method will be conducted for FEV1, FVC and pulse oximetry changes at preoperative day 3 from day 1. The frequency of use, defined as the daily number of times patients perform incentive spirometry, will be compared across all groups in the postoperative setting using ANOVA or Kruskal-Wallis test, as appropriate. For postoperative complications, Chi-square test will be used to test the differences between six groups. The univariate logistic regression model will estimate the odds ratio of postoperative complication. Multivariate analysis through stepwise selection will be considered to examine the relationship between binary outcome and independent predictors, where a significance level of 0.3 is required to allow a predictor into the model, and a significance level of 0.35 is required for a predictor to stay in the model. All analyses will be conducted using SAS (SAS Institute, Cary, NC) at the two-sided 5% significance level.

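### Section 9.5 appears to split the primary alpha over three pairwise contrasts when the primary objective needs two; the cost is about 4 points of power per contrast, with no error in the stated power or in type I control

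*Combined protocol and SAP*

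**What the plan says.** - **Objective.** Section 9.1: "The primary objective of this study is to determine the efficacy of incentive spirometry to improve FEV1 in the preoperative setting". The Synopsis and Section 2.0 agree. The comparator is a no-IS control arm, and there are two IS arms, standard and digital plus text message.
- **Sizing.** Section 9.5: "Bonferroni correction will be used for three-group comparisons". The calculation is made "assuming a mean difference of 0.4 L and a standard deviation of 0.6 at a significance level of 0.017", "using a two-sided, two-sample, equal-variance t-test", and concludes: "Sample sizes of 49 per group achieve 80.6% power to detect the difference in FEV1".
- **Source of the effect.** Section 9.5 takes from earlier research that "the mean difference in FEV1 between control and preoperative incentive spirometry intervention groups is 0.4 L with a standard deviation of 0.6". The figure is therefore for IS against control.
- **Digital against standard.** The third exploratory objective, in both the Synopsis and Section 2.0, begins "To evaluate whether a digital IS device + text message based mobile health intervention will improve FEV1" and names standard IS as the comparator.
- **Analysis.** Section 9.6 compares the change in FEV1 across the three groups by ANOVA or Kruskal-Wallis. It mentions neither pairwise tests nor the Bonferroni step, and ends: "All analyses will be conducted using SAS (SAS Institute, Cary, NC) at the two-sided 5% significance level".

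No section lists the pairwise contrasts behind the 0.017 or calls any set of contrasts confirmatory.

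**The concern.** The primary question, whether IS improves preoperative FEV1, is answered by two contrasts: standard IS against control and digital IS against control. The level of 0.017 corresponds to three. On that reading a third of the 5% is reserved for digital against standard, which the objectives class as exploratory, and the two primary contrasts are tested more strictly than error control requires.

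What is at stake is efficiency: some power for the primary question, or equivalently a few patients. The sponsor can recover it by wording alone, because the objectives already place the third contrast outside the primary question.

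**Working it through.** **Inputs (Sections 9.1 and 9.5).** Difference 0.4 L; SD 0.6; 49 evaluable per arm; 1:1:1 allocation; two-sided equal-variance t-test; level 0.017; 5% dropout.

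**1. Reproduce the plan's figure.** The noncentrality is δ = 0.4 / (0.6 × √(2/49)) = 0.4 / 0.1212 = 3.30, with 2 × 49 − 2 = 96 degrees of freedom. At 0.017 the critical t is 2.429 and the exact noncentral-t power is 80.6%, as stated. At exactly 0.05/3 = 0.01667 it is 80.4%. Enrolment is 49/0.95 = 51.6, rounded up to 52, and 3 × 52 = 156, as stated.

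**2. Change only the family.** With two contrasts the Bonferroni level is 0.05/2 = 0.025. The critical t becomes 2.277 with the same δ, and power is 84.5%, a gain of 84.5 − 80.6 = 3.9 points. Alternatively, 80% power at 0.025 needs 45 per arm: 45/0.95 = 47.4, so 48 enrolled per arm and 144 in all, 12 fewer than 156.

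**3. Separate the family from the procedure.** Simulation with 49 per arm, SD 0.6 and variance pooled over the three arms. This pooling puts the single-contrast figures slightly above the exact two-sample values.

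| | Three-way Bonferroni (0.017) | Two contrasts, Bonferroni (0.025) | Two contrasts, Holm |
|---|---|---|---|
| Both IS arms gain 0.4 L: power per contrast | 81% | 85% | 89% |
| Both IS arms gain 0.4 L: both contrasts succeed | 70% | 76% | 84% |
| Only one arm gains 0.4 L: power for that arm | 81% | 85% | 85% |
| No effect: any false positive over the two control contrasts | about 3.1% | about 4.6% | about 4.6% |

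Of the 8-point gain per contrast (81% to 89%), about 4 points come from the smaller family and 4 from Holm. Of the 14-point gain for both (70% to 84%), about 6 come from the family and 8 from Holm. The Holm part depends on both arms working.

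**4. Error control.** Under the three-way split, about 3.1% of the 5% is used on the two primary contrasts. Holm over two uses about 4.6%. When one arm works and the other does not, the false-positive rate for the inactive arm under Holm is about 4.3% to 4.4%, also below 5%.

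**The case against.** **Nothing falls short.** The trial was sized at 0.017 and reaches 80.6% there. All-pairwise Bonferroni in a three-arm trial is conventional and errs on the safe side. This stands, and it limits the weight of the point.

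**The family is inferred.** Section 9.5 lists no contrasts. This also stands. The match of 0.017 to 0.05/3 with three arms makes the inference reasonable, but the text does not confirm it.

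**The status of the third contrast is not uniform.** The Synopsis and Section 1.2 hypothesise that the digital device with text messages will improve prehabilitation, and the exploratory objectives listed in Section 9.1 omit the contrast. A sponsor could reasonably want it protected. That is a fair alternative, but then the objectives should promote it openly. The Synopsis and Section 2.0 now class it as exploratory.

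**The loss may never occur.** Section 9.6 has only an omnibus test at 5%, so the split matters only if the pairwise tests implied by 9.5 are the confirmatory analysis. This stands. It is also a reason to settle the contrasts in both sections, since carrying 9.5 into 9.6 unchanged would keep the three-way split.

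**The third contrast can be kept cheaply.** A 5% ANOVA followed, if significant, by 5% pairwise tests gives about 88.6% per contrast and 83.9% for both when both arms gain 0.4 L, with global-null error of 5.0%, and retains digital against standard. This is a sound alternative, but the plan does not state it.

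**A stronger reading.** A reader might infer that the 80.6% is wrong because it does not hold for digital against standard. The plan never claims that it does: Section 9.5 ties the 0.4 L to control against IS.

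**Conclusion.** The point holds as a conservative inefficiency. Section 9.5 appears to share the primary alpha over three contrasts when its own objective and planning effect call for two. Correcting the family alone is worth 3.9 points per contrast (80.6% to 84.5%), about 6 points for both contrasts, or about 12 enrolled patients. Adding Holm brings the figures to about 89% and 84% if both arms gain 0.4 L, and about 85% for the effective arm if only one does.

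This assumes that 0.017 stands for all three pairs, that the pairwise tests are the confirmatory analysis, and that the plan's 0.4 L, SD 0.6 and 49 evaluable per arm are right.

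Three stronger conclusions are not supported. The trial is not underpowered against its stated 80.6%. Type I error is not inflated. The full rise to 89% and 84% cannot be put down to the choice of family, since about half of the per-contrast gain and more than half of the joint gain come from Holm. The change is worth making because it is cheap, but the validity of the trial does not depend on it.

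**What to change.** In Sections 9.5 and 9.6:

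1. Name two confirmatory contrasts on the change in FEV1 from baseline to the day of surgery: standard IS against control, and digital IS against control.
2. Make the primary analysis a Holm test of these two (smaller p-value at 0.025; if it succeeds, the other at 0.05), in place of the omnibus-only test.
3. Restate power for these two contrasts only, giving the assumption about whether one or both arms work.
4. Report digital against standard on FEV1 as exploratory, with an estimate and confidence interval.

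The cost is revised wording and a new power sentence, with no added patients or data. The downside is that digital against standard has no confirmatory test. If the sponsor wants one, the objectives must say so and the multiplicity plan must include it explicitly.

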9.6 Data Analysis

The analysis will be intent-to-treat approach. The FEV1, FVC and pulse oximetry changes at day-of-surgery preoperative from baseline will be compared across three groups using ANOVA or Kruskal-Wallis test, as appropriate. The linear regression model will be considered to adjust for the other interested variables including age, sex, smoking status, BMI, ASA, and malignancy. The same analysis method will be conducted for FEV1, FVC and pulse oximetry changes at preoperative day 3 from day 1. The frequency of use, defined as the daily number of times patients perform incentive spirometry, will be compared across all groups in the postoperative setting using ANOVA or Kruskal-Wallis test, as appropriate. For postoperative complications, Chi-square test will be used to test the differences between six groups. The univariate logistic regression model will estimate the odds ratio of postoperative complication. Multivariate analysis through stepwise selection will be considered to examine the relationship between binary outcome and independent predictors, where a significance level of 0.3 is required to allow a predictor into the model, and a significance level of 0.35 is required for a predictor to stay in the model. All analyses will be conducted using SAS (SAS Institute, Cary, NC) at the two-sided 5% significance level.

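### Section 9.6 does not carry the pairwise 0.017 test of Section 9.5 into the primary FEV1 analysis, and its blanket 5% level contradicts it

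*Combined protocol and SAP*

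**What the plan says.** Section 9.1 sets the aim: "The primary objective of this study is to determine the efficacy of incentive spirometry to improve FEV1 in the preoperative setting".

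Section 9.5 ties the sample size to that endpoint: "The sample size calculation is based on the primary outcome only". The effect is a comparison with control: "the mean difference in FEV1 between control and preoperative incentive spirometry intervention groups is 0.4 L", with SD 0.6. It then commits to an adjustment, "Bonferroni correction will be used for three-group comparisons", and computes power "at a significance level of 0.017 using a two-sided, two-sample, equal-variance t-test". The result is 80.6% power with 49 per group, raised to 52 per group (156 in total) for 5% dropout.

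Section 9.6 gives the analysis. The change in FEV1 at day-of-surgery "preoperative from baseline will be compared across three groups using ANOVA or Kruskal-Wallis test", whichever is appropriate. A linear regression adjusting for age, sex, smoking status, BMI, ASA and malignancy is to be considered; no treatment contrast or level is given for it. The section closes: "All analyses will be conducted using SAS (SAS Institute, Cary, NC) at the two-sided 5% significance level". It mentions no pairwise comparison, no Bonferroni correction and no 0.017 level.

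The synopsis places the comparison of the two IS arms among the exploratory objectives: whether a "digital IS device + text message based mobile health intervention will improve FEV1, FVC, and pulse oximetry compared to standard IS".

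**The concern.** The test that was powered and the test that is specified differ in form and in level. The powered test compares two arms at 0.017. The specified test asks at 5% whether any of three arms differs from the others.

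The primary objective is directional: IS should improve FEV1. A significant three-group test shows that some arm differs. It does not show which one, in which direction, or whether the difference involves control at all. It could be driven by digital against standard IS, which the synopsis treats as exploratory.

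The level for a pairwise claim is also unsettled. Section 9.5 implies 0.017, while 9.6 says 5% for everything, without exception. If that is settled only after the data are seen, the choice of level is no longer pre-specified.

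**Working it through.** **Inputs.** From 9.5: 49 per arm, difference 0.4 L, SD 0.6, two-sided 0.017 (0.05/3 = 0.0167, rounded). From 9.6: three-group ANOVA at 5%. Assumed, because the documents give no pattern of arm means: normal data and the means stated below, in the order control, standard, digital.

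**1. The plan's own figure.** SE of a difference = 0.6 × √(2/49) = 0.1212 L. Noncentrality = 0.4/0.1212 = 3.30 on 96 df. Noncentral t power at 0.017 is 80.6%, as stated. Dropout: 49/0.95 = 51.6, so 52 per arm and 3 × 52 = 156. Both reproduce.

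**2. The test that 9.6 states.** Noncentral F with λ = n Σ(μᵢ − μ̄)²/σ². For (0, 0.4, 0.4), Σ(μᵢ − μ̄)² = (2/3) × 0.16 = 0.1067, so λ = 49 × 0.1067/0.36 = 14.5 on 2 and 144 df. Power at 5% is 93.2%. It is the same for (0, 0, 0.4), where only the digital arm works: the omnibus test cannot tell these two situations apart. For (0, 0.2, 0.4) it is 84.1%.

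**3. What a significant omnibus result leaves open.** Simulation, 400,000 trials per pattern; above control means significant in the IS direction at two-sided 0.017.

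| Means (L) | Omnibus significant, neither IS arm above control |
|---|---|
| 0, 0.4, 0.4 | 1.8% |
| 0, 0, 0.4 | 12.7% |

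Within the 12.7%, digital versus standard is significant at 0.017 in 10.9% of all trials. There the primary test would be positive mainly on the strength of an exploratory comparison.

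**4. Family-wise error, no true differences (simulation).**

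| Reading | Family-wise error |
|---|---|
| Three ungated pairs at 5% | 12.2% |
| Two ungated pairs against control at 5% | 8.9% |
| Three ungated pairs at 0.017 | 4.5% |
| ANOVA at 5%, then pairs at 5% | 5.0% |

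**5. Where the two levels disagree for a pair.** The smallest significant observed difference at SD 0.6 is 1.985 × 0.1212 = 0.241 L at 5%, and 2.429 × 0.1212 = 0.294 L at 0.017. The band from 0.24 to 0.29 L exists only on the reading in which pairs are tested at 5%. The ANOVA itself (critical F = 3.06) needs √(3 × 3.06 × 0.36/49) = 0.26 L between the extreme arms when the third arm equals one of them, and √(4 × 3.06 × 0.36/49) = 0.30 L when the third lies midway.

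**6. Gating.** Requiring a significant ANOVA before reading the pairs at 0.017 changes whether any IS arm beats control in 0.1% to 0.9% of trials across (0, 0.4, 0.4), (0, 0, 0.4), (0, 0.2, 0.4) and (0, 0.3, 0.3).

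**The case against.** The best defence is that protocol and analysis plan are one document, so the Bonferroni commitment in 9.5 binds. Since 0.017 is 5%/3, the 5% in 9.6 can be read as the family level, with 9.5 governing the pairs. ANOVA followed by Bonferroni pairs is a familiar sequence, and any ANOVA-gated reading keeps family-wise error near 5%. The regression in 9.6, with control as reference, would also give each IS arm's signed difference from control.

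Much of this stands: pairs at 0.017 are the likely intent. But 9.6 applies 5% to all analyses without calling it a family level, states no gate, and offers the regression only as something to consider. Nothing elsewhere links the two sections.

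Three stronger readings are tempting, and the documents do not support them.

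- A reader might infer that the trial is underpowered. It is not: the stated omnibus test has more power under the plan's effect (93.2%) than the pairwise test it was sized on (80.6%).
- A reader might infer that type I error is inflated. That holds only if pairs are tested at 5% with no gate, which 9.6 permits but does not prescribe.
- A reader might blame the wording for trials in which only one of two effective arms beats control. With both arms truly 0.4 L better and pairs tested at 0.017, at least one arm beats control in 91.7% of trials and both in 69.6%, so 91.7 − 69.6 = 22.1% show one arm only. That follows from power per pair, and the fix leaves it unchanged.

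**Conclusion.** The inconsistency is real and should be corrected, but it is one of specification, not of design. Read literally, 9.6 gives a primary result that names neither arm nor direction, and a level that contradicts 9.5 for any pairwise claim.

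The consequence depends on the truth. It is small if both IS arms gain 0.4 L (1.8% of trials have a positive omnibus test and no IS arm above control) and material if only the digital arm does (12.7%). Literal use of 5% for ungated pairs would put family-wise error at about 12% for three pairs or 9% for two, against 4.5% for three pairs at 0.017. These figures assume 49 evaluable patients per arm, SD 0.6, normal data and the mean patterns shown. They describe the ANOVA, not the Kruskal-Wallis alternative. The sample size calculation in 9.5 is sound.

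**What to change.** In Section 9.6, for the FEV1 primary endpoint:

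- State that the efficacy conclusion rests on standard IS versus control and digital IS versus control, each at the two-sided 0.017 level of 9.5. Use the two-sample t-test, or a rank-based two-sample test where Kruskal-Wallis would have been used.
- Exempt these comparisons from the closing 5% sentence.
- Label the three-group ANOVA or Kruskal-Wallis a supportive global test at 5%.
- Keep digital versus standard as the third pair in the 0.05/3 family, reported as exploratory in line with the synopsis.
- State in advance whether the omnibus test gates the pairs. Either choice is defensible and belongs to the sponsor; it changes under 1% of results.

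Section 9.5, N=156, data collection and conduct are unaffected. The one cost is that a pairwise claim must meet 0.017 (about 0.29 L observed at SD 0.6) where a 5% reading would accept about 0.24 L. That is the level the trial was already sized for.

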There is emerging field of study to evaluating IS in the **preoperative** setting which have yielded mixed results.^{23,26,27} A 2010 study from Kundra et al. evaluated the effect of preoperative IS on patients undergoing laparoscopic cholecystectomy and failed to show any differences in preoperative PFTs compared to baseline in the control group, while patients in the intervention group had a 11.9% increase in FEV1 and 12.1% increase in FVC compared to baseline.²⁸ Additionally, Fulop et al evaluated the use of IS 4-5 times daily before undergoing colorectal surgery in which the intervention group had improved inspiratory capacity compared to baseline, compared to the control group in which the inspiratory capacity remained the same (113% vs 100% of baseline value).²⁹ Similarly, a group from India reported their results of preoperative IS regimen consisting of 15 mins of IS every 4 hrs for 7 days before surgery, compared to standard of care.³⁰ Preoperative control peak expiratory flow rate (PEFR) was not different between groups, and postoperatively they only found a statistically significant difference on postoperative day

2 (69.48% intervention vs 61.66% control of baseline PEFR). In all the preoperative studies there was no statistically significant differences in postoperative morbidity and mortality.

In summary, there is a significant knowledge gap and methodological concerns regarding the benefits of IS use across the continuum of surgical care. As reported above, there is a substantial variance in IS specific measurements and outcomes evaluated across many surgical studies in the preoperative and postoperative period. An important, and unaddressed, methodological issue with the current data available is the lack (and unreported) data pertaining to the compliance of patients using the IS as intended.²³ Most protocols reported in the literature detail the patient IS instructions/protocol ranging from IS use at 4-5 times per a day up to 10 times per hour but fail to objectively evaluate and adjust their analyses to patients successful completing the IS protocol.³¹⁻³³

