1.2 Study Design

The goal of this study is to determine the efficacy of IS to improve pulmonary function in the preoperative and postoperative surgical setting. We hypothesize that IS will improve pulmonary function for patients undergoing major abdominal surgery when controlling for protocol compliance. Additionally, we hypothesize that a digital IS device + text message based mobile health intervention will improve pulmonary pre-habilitation and rehabilitation, as well as postoperative compliance with the IS device.

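### The only postoperative lung-function comparison with defined time points starts from POD1, so it cannot show a benefit of preoperative spirometry already present that day

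*Combined protocol and SAP*

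**What the plan says.** Section 1.2 states the goal as "to determine the efficacy of IS to improve pulmonary function in the preoperative and postoperative surgical setting". Section 9.1 extends the secondary efficacy objectives to "FEV1, FVC, and pulse oximetry in the postoperative setting".

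The matching secondary endpoint, in the Synopsis and section 2.0, is "Change in FEV1, FVC and pulse oximetry at postoperative day 3 from day 1". Sections 9.4 and 9.6 name the same endpoint but call the later time point preoperative day 3. The schedule has no such measurement, so this is a slip for postoperative day 3.

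For the analysis, section 9.6 first says that the changes from baseline to the day of surgery "will be compared across three groups using ANOVA or Kruskal-Wallis test, as appropriate", with linear regression considered for adjustment. It then says: "The same analysis method will be conducted for FEV1, FVC and pulse oximetry changes at preoperative day 3 from day 1". Only the preoperative randomisation has three groups. The second randomisation, on POD1, has two. Section 9.6 does not say how the second assignment enters this analysis.

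Section 9.3 confirms that "FEV1, FVC, and pulse oximetry will be obtained for all patients at 4 different time points": enrolment, the day of surgery before the operation, 24 hours after surgery, and POD3. No POD1 or POD3 value is compared with the enrolment or day-of-surgery value in any endpoint that states its time points.

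**The concern.** The preoperative intervention ends before surgery, so for the three preoperative arms the POD1 value is an outcome of treatment and not a baseline. If preoperative spirometry works as the primary hypothesis supposes, part of its effect may already be visible on POD1, as a higher starting level or a smaller surgical fall. Taking POD1 as the reference subtracts that effect and leaves only recovery over the next two days.

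What is at stake is how a secondary result is read. A null POD1-to-POD3 comparison could be reported as no postoperative lung-function benefit from preoperative spirometry when the benefit had been differenced out. A comparison favouring control could be reported as harm when the treated arm was better on both days and its advantage had only narrowed. Section 1.1 describes a preoperative trial that gave its postoperative day 2 result as a percentage of baseline peak expiratory flow rate (69.48% against 61.66%). That reference point is missing from this plan's postoperative endpoint.

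**Working it through.** **Inputs.** From section 9.5: mean difference 0.4 L, SD 0.6 L, 49 evaluable per group, two-sided alpha 0.017, two-sample equal-variance t-test, stated power 80.6%, 5% dropout, 52 per group, 156 in total. The documents give no postoperative effect and no SD for any postoperative change, so everything after step 1 is illustrative.

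**1. The plan's own figure.** The noncentrality is d / (SD × √(2/n)) = 0.4 / (0.6 × √(2/49)) = 3.30, with 2 × 49 − 2 = 96 degrees of freedom. The exact noncentral-t power is 80.62%, matching the stated 80.6%. For dropout, 49 / 0.95 = 51.6, which rounds up to 52, and 52 × 3 = 156. The sample-size figures reproduce.

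**2. What the planned contrast estimates.** Let b1 and b3 be the mean advantage of a spirometry arm over control at POD1 and POD3. The between-arm difference in (POD3 − POD1) is b3 − b1. This is algebra and needs no clinical assumption. The difference in (POD1 − baseline) is b1 and in (POD3 − baseline) is b3, because randomisation equalises expected baseline values.

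**3. Illustrations** (49 per arm; SD 0.6 L assumed for every change; alpha 0.017):

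| b1 (L) | b3 (L) | Planned contrast b3 − b1 (L) | Rejection, planned | Power, baseline to POD1 | Power, baseline to POD3 |
|---|---|---|---|---|---|
| 0.4 | 0.4 | 0 | 1.7% | 80.6% | 80.6% |
| 0.4 | 0.2 | −0.2 | 22.3%, sign reversed | 80.6% | 22.3% |
| 0 | 0.4 | +0.4 | 80.6% | 1.7% | 80.6% |

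In the first row the 1.7% is alpha itself and does not depend on the SD. In the last row the planned contrast works as intended.

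**4. Sensitivity to the assumed SD.** For a baseline-anchored contrast of 0.4 L, power is 99.4% at SD 0.4 L, 80.6% at 0.6 L and 52.1% at 0.8 L.

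**5. Sensitivity to alpha.** Section 9.6 sets analyses at 5%. For the three-group ANOVA at 0.05 with SD 0.6 L, simulation gives about 5% rejection when the benefit is constant from POD1. It gives about 93% for a baseline-anchored change with both spirometry arms 0.4 L above control. The conclusion does not depend on which alpha is used.

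**The case against.** The strongest reply is that the POD1-to-POD3 change was meant for the second randomisation. That assignment is made on POD1, so POD1 is its natural reference, and secondary objective 2 in the Synopsis speaks only of change after surgery without naming the preoperative arms. This partly stands: the three-group reading is inferred from the words about using the same method, not stated outright. But section 9.6 does not restrict the analysis to the re-randomised groups. If that restriction was intended, the preoperative arms have no time-defined postoperative lung-function comparison at all. The text needs changing on either reading.

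It can also be said that two-day recovery is a legitimate quantity and not a biased estimate of another one. That stands. The difficulty is only that it does not answer the question of carried-over benefit.

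A reader might infer that this is the only postoperative comparison of the preoperative arms. It is not. Complications are compared across the three preoperative groups (Synopsis, 9.1) or six groups (2.0, 9.6), and postoperative frequency of use is compared across all groups (9.6). The Synopsis also lists an exploratory difference in lung-function changes between randomised groups. The first two are not lung function, and the third gives no time points and has no analysis of its own in 9.6.

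A reader might also want a power loss under proportional surgical decline. If FEV1 fell to 50% on POD1 and recovered to 70% on POD3 (assumed), a 0.4 L difference becomes 0.20 L and 0.28 L, so the change differs by 0.08 L. Power is about 4% if the SD stays at 0.6 L. If the SD scales too (0.2 × 0.6 = 0.12 L), the ratio 0.08/0.12 = 0.667 equals 0.4/0.6 and power is again 80.6%. The documents cannot decide between these, so no weight is placed on that scenario.

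**Conclusion.** The point holds in a limited form. The one postoperative lung-function comparison with defined time points measures recovery from POD1 to POD3. Applied to the three preoperative arms, it cannot show a benefit already present on POD1, and it turns a waning benefit into an apparent disadvantage. That follows from the definition of the contrast. The power figures rest on an assumed postoperative effect of 0.4 L and an assumed SD, with a range of 52.1% to 99.4% for SDs from 0.8 L down to 0.4 L.

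It would be too strong to say that the endpoint cannot show any postoperative effect of preoperative spirometry: a 0.4 L benefit arising only after POD1 would be detected with 80.6% power at SD 0.6 L. Nor is the enrolment baseline unused in the plan, since it anchors the primary endpoint and the first secondary endpoints. Those endpoints and the sample size, which section 9.5 bases on the primary outcome alone, are unaffected. This is a worthwhile and cheap correction to a secondary endpoint. It does not threaten the primary result.

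**What to change.** In sections 2.0, 9.4 and 9.6, and in the Synopsis to match:

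- Add, as secondary endpoints for the three preoperative arms, the change from enrolment baseline to POD1 and from enrolment baseline to POD3 in FEV1, FVC and pulse oximetry. ANCOVA on the POD1 and POD3 values with baseline as covariate would serve equally well.
- Include the postoperative assignment as a factor in the POD3 model, because POD3 follows the second randomisation.
- State that the POD1-to-POD3 change is for the re-randomised digital-versus-standard comparison.
- In 9.4 and 9.6, correct the time point from preoperative to postoperative day 3.

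The cost is wording and multiplicity. Three measures at two times give 3 × 2 = 6 secondary contrasts for the preoperative arms, besides the three kept for the second randomisation (9 in all, against 3 now). They should be reported as secondary, with the multiplicity acknowledged. All four measurements are already scheduled for every patient, so no visits, tests or patients are added.
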